Auditory stimulus consists of a brief burst of white noise, lasting approximately 100 ms. Visual stimulus is a white colored orb positioned against the dark, neutral background and will be displayed for 1-2 seconds. The longer duration of the visual stimulus will serve to provide stimulus location feedback for patients. Patients will be instructed to orient their eyes and head toward stimuli in the hemianopic field and to push a button on a controller upon detecting stimuli. This part of the task will serve to boost motivation and maintain attention during training. The software will also record these responses and reaction times, based on the button presses, and store this data for later review. The next trial will begin 3-4 seconds after the visual or auditory-visual stimulus disappears and when the patient re-fixates on the fixation point.

Cross-modal visual auditory rehabilitation consists of a total of 200 trials / day (about 30 min) over 1 month. Given the results from animal model studies, we expect progress to be observable after 2-3 weeks of cross-modal rehabilitation, and completion of rehabilitation 1 month after the start of cross-modal training.

While we expect most patients will perform rehabilitation using the virtual reality rehabilitation system, patients may also complete rehabilitation with a free-field frame device if they are not comfortable with using a VR headset. The free-field frame device uses a semi-circular frame to hold LED lights (visual stimulus) and speakers (auditory stimulus) in front of the patient. These lights and speakers can be used to deliver the same cross-modal visual auditory rehabilitation paradigm. The device is also used to perform peripheral visual field tests, and is described in more detail below in *peripheral visual field test*.

Tests

Humphrey Visual Field (HVF) Test - The HVF test is a common test given to map the visual field. During the HVF test, light is projected into a white bowl with a standardized background light intensity to form a circular stimulus, around 30 cm away from the patient's eye. The overall field mapping technique used is a form of static perimetry, where a stimulus appears in various areas of the field of vision. The patient indicates when they can see the stimulus and the perimetrist then records the point where the stimulus was seen. These datapoints are used to determine the patient's visual field.

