Peripheral Visual Field Test - Since the Humphrey visual field test only measures up to 30° in the periphery, an additional peripheral visual field test will be administered using a semi-circular frame device (fig. 1) set 50 cm in front of the subject with LED lights acting as visual stimulus, located at azimuths of 15°, 30°, 45°, 60°, and 75°, as well as a center fixation light. Lights will be presented at a random time with a fixation period between each trial and locations selected randomly. Subjects will be asked to fixate on the center fixation light while lights are presented at random locations at random times (0-1.5 seconds). Upon detecting a light, subjects will press a button. Subject responses will be used to determine how far in the periphery, up to 75°, a subject can see. The test will present a total of 5 trials at each location in both the intact and hemianopic side, as well as 5 trials with no stimuli.

This test uses the free-field frame device to position visual and auditory stimuli, in the form of LED lights and speakers, at different angles of the patient. The patient is asked to maintain visual fixation on a lit LED light straight ahead during the test. Speakers will play a brief burst of white noise from a random location 15° or 45° on either the left or right side. The subject will be asked to identify where the sound is originating from either verbally or using a button response pad. During this test, subjects' eyes may be videotaped or photographed. These recordings or photos will be reviewed by a member of the study team to confirm the subject is able to properly maintain visual fixation.

Figure 1: Free-field frame device

track rehabilitation progress. The test consists of 30 trials with visual stimulus presented either 15°, 30°, 45° in either the hemianopia field or the intact field at random time intervals.

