Testing: Possessing the ability to localize sound is essential in properly implementing the rehabilitation strategy, which relies on subjects to respond to auditory and visual training stimuli. As part of the screening process, subjects' ability to detect the approximate location of sound will be assessed. Subjects will be asked to fixate on a light straight ahead and be presented with sound from 15° or 45° on either the left or right side. The location of the sound will be randomly picked by a computer program. Subjects will be asked to identify the side the sound originated from and the approximate location. Study staff will log these responses on a computer. Subjects with responses accurate 90% or higher will be considered to have passed the test and be eligible for the study.

This test will be conducted using the free-field frame device (fig 1), which uses a semicircular frame to hold LED lights and 4 speakers fixed to 15° and 45° positions. Eye tracking or a camera recording of the subject's eyes may be used to ensure the subject is properly fixating on the light. The eye tracking camera may take photographs and video for the study team to later review. If a subject cannot maintain visual fixation or identify the origin of sound, the visit and study will end and they will be compensated \$40 for their travel.

[figure not shown]

Figure 2: Study Timeline

To verify their hemianopia condition, subjects will be asked to provide relevant medical records, which will be used to confirm diagnosis. Subjects will be instructed to bring their medical records, with proof of hemianopia diagnosis, to the screening visit. After they have passed the sound localization and visual fixation test, a study member will review these records to make sure the subject is eligible to continue the study. Since the effects of hemianopia can vary between patients due to the extent and location of brain damage, copies of relevant records may be kept to aid data analysis. These copies will be kept in a locked and secure storage location. Patients will be assigned a subject id and any identifying personal information will be redacted from these copies. If the patient is deemed ineligible during the study, any copies made of these records will be promptly destroyed.

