Study Session 35: 3 Month Post-Intervention Follow-up Tests (1 hour)

Subjects will complete a follow-up visit 3 months after the end of rehabilitation on the Wake Forest Baptist Medical Center campus. The follow-up visit will consist of a peripheral visual field test, and NEI VFQ-25 and VA LV VFQ-48 questionnaires.

Study Session 36: 6 Month Post-Intervention Follow-up Tests (1 hour)

Subjects will complete a final follow-up visit 6 months after the end of rehabilitation on the Wake Forest Baptist Medical Center campus. The follow-up visit will consist of a peripheral visual field test, and NEI VFQ-25 and VA LV VFQ-48 questionnaires.

Outcome Measure(s)

The primary outcomes for all participants will be the visual field measurements from Humphrey Visual Field and peripheral frame test, with comparisons made before (visits 1 and 2) and after treatment (visits 34 and 35 or visits 63 and 64).

Secondary outcome measures will include differences in quality of life questionnaire results from before (visit 1) and after treatment (visit 33 or 63) and changes in VR progress test results during the course of rehabilitation (visits 3-32 and 33-62 if a subject repeats rehabilitation).

Exploratory outcome measures will be collected in subjects with restored visual fields. The qualities of recovered visual field will be examined with visual acuity, color recognition, and shape recognition tests after rehabilitation (visit 33 or 63).

Analytical Plan

Results will be analyzed initially using descriptive statistics. The improvement of visual detections will be assessed by using a two-way ANOVA on the percentages of visual detections to stimuli presented in the hemianopic hemifield in the peripheral visual field tests before and after rehabilitation. Comparisons for subjects will be done using chi square tests for proportions, and t-tests or ANOVA procedures for continuous variables. Other inferential statistical analysis will be conducted as appropriate.

Human Subjects Protection

Subject Recruitment Methods

Protocol version: 2

Protocol updated 7.01.20

Subjects with homonymous hemianopia on either the left and right side of the visual field will be recruited using resources from Wake Forest University Health Sciences' Clinical and Translational Science Institute (CTSI). Members of the PI's research team will perform recruitment. Coordination of potential participants' visit will be done by phone or in person conversation or by email.

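### Gaze is not verified on the post-training peripheral frame test, so a gaze shift toward the blind side could count as recovered field

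*Combined protocol and SAP*

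**What the plan says.** All references are to the combined protocol and SAP.

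- **Outcome Measure(s):** "The primary outcomes for all participants will be the visual field measurements from Humphrey Visual Field and peripheral frame test", compared before and after treatment.
- **Analytical Plan:** improvement is to be assessed by a "two-way ANOVA on the percentages of visual detections to stimuli presented in the hemianopic hemifield in the peripheral visual field tests", comparing the pre-training and post-training results. Humphrey perimetry is not named in that analysis.
- **Tests, Peripheral Visual Field Test:** "Subjects will be asked to fixate on the center fixation light while lights are presented at random locations at random times (0-1.5 seconds". Scoring: "Upon detecting a light, subjects will press a button". The paragraph adds a fixation period between trials, random locations and 5 trials with no light. It sets no condition on gaze for a press to count.
- **Next paragraph under Tests:** "During this test, subjects' eyes may be videotaped or photographed", with review by a study-team member. The task in that paragraph is auditory: "The subject will be asked to identify where the sound is originating from either verbally or using a button response pad".
- **Study Session 1, Sound Localization and Visual Fixation Testing:** "Eye tracking or a camera recording of the subject's eyes may be used". This is a screening step. Good fixation on the training task is also an inclusion criterion.
- **Study Sessions 3–32:** eye tracking in the training headset is likewise something that *may* be fitted.
- **Interventions:** "Patients will be instructed to orient their eyes and head toward stimuli in the hemianopic field". The 9:1 ratio of blind-side to intact-side stimuli is meant to shift attention to the blind field. Each training trial starts with 1 second of central fixation, and the next one waits for re-fixation.

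**The concern.** The Background sets this therapy apart from oculomotor compensation, which helps patients manage the loss without recovering the field. The primary test therefore has to tell the two apart. A button press shows that a light was seen, but not where the eyes were pointing when it was seen.

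The only stated fixation checks come at entry, before training. Training then rehearses eye and head movement toward the blind side, so fixation at screening is weak evidence about fixation afterwards. If some subjects come to look toward the blind side during the test, post-training detections rise with no change in the field. The error favours the hypothesis, and with no control group nothing in the comparison offsets it. The study's response data are meant to inform future studies, so the error would carry forward.

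**Working it through.** **Plan's own figure.** The plan gives no number on fixation. Its one precision figure, a half-width of 0.35 for an 80% success rate with n = 5, reproduces as 1.96 × √(0.8 × 0.2 / 5) = 0.351. It has no bearing on this point.

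**What each safeguard would catch.**

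| Safeguard in the plan | What it does | What it leaves open |
|---|---|---|
| Fixation at entry | Selects subjects able to fixate | Behaviour after training |
| Fixation instruction and fixation period | Encourage central gaze | Whether gaze was central at onset or before the press |
| Random side and onset | Limit the gain from guessing | A bias toward one side, or a search |
| 5 blank trials | Detect presses without a light | A real light seen after a shift |
| Re-fixation in training | Rehearses return to centre | Gaze during the test |

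None of these verifies gaze on a post-training test trial.

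**Illustration of size.**

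Inputs from the Peripheral Visual Field Test: lights at 15, 30, 45, 60 and 75 degrees, with 5 trials per location per side. That is 5 × 5 = 25 hemianopic trials and, with the intact side and blanks, 5 × 5 × 2 + 5 = 55 trials per test.

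Assumptions that are not in the documents:
- no recovered field, with the field border at the vertical midline;
- certain detection of a light at or inside the gaze line;
- no such shifts at baseline;
- gaze turned g degrees toward the blind side on a share q of trials.

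Let k be the number of hemianopic azimuths at or below g. Spurious detection = 100 × q × k/5.

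| Shift g | k | q = 1/4 | q = 1/3 | q = 1/2 | q = 1 |
|---|---|---|---|---|---|
| 15° | 1 | 5% | 6.7% | 10% | 20% |
| 30° | 2 | 10% | 13.3% | 20% | 40% |
| 45° | 3 | 15% | 20% | 30% | 60% |

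**Could intact-side trials reveal it?** A shift of g moves an intact-side light at a degrees to a + g from the gaze line. With a 45° shift, the 60° and 75° lights move to 105° and 120°, so misses there might expose a sustained large shift. With a 15° shift, the farthest light is at 75 + 15 = 90° and the others are closer, so a modest shift may leave the intact-side score nearly unchanged. A search that begins only when nothing has been seen would not affect intact-side trials at all.

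**The case against.** The strongest counter-argument concerns mechanism. Training teaches orienting toward a stimulus that is presented with a sound at its location, on predictable timing. The frame test, as described, uses lights alone at a random side and time, and a subject with no recovered field cannot orient to a light that is not seen. This stands, and it narrows the concern to two routes: an anticipatory shift before onset, or a search while the light is on. The plan does not exclude either. It is also unclear whether the 0–1.5 seconds is an onset delay or a light duration; a long duration would make searching easier.

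Training also rehearses return to centre on every trial, so it is not only practice in looking away. Shifts already present at baseline would partly cancel in a before/after difference. Humphrey perimetry is a separate primary measure, but the plan states no fixation check for it, it reaches only 30°, and it is not scheduled at 3 or 6 months. The study is exploratory and hopes for at least 5 completers, which bears on severity.

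Three stronger readings are tempting and not supported:

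- *Eye recording is absent from the frame test.* The recording sentence probably belongs to the sound-localization task, but paragraph order there is disturbed. The documents support only that recording is optional at most.
- *The bias is 20, 40 or 60%.* Those are levels under assumed shift sizes and frequencies, not estimates.
- *Subjects complete 200 × 0.9 × 30 = 5,400 blind-side orienting trials before the post-test.* Training may end once 45° is reliably detected, may be repeated for a second month, and may be interrupted or restarted. The count also says nothing about gaze during the test.

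**Conclusion.** The concern holds as a measurement gap. On the primary variable named for analysis, the plan does not verify gaze after an intervention that trains gaze movement toward the blind side, and no rule covers trials on which gaze moved. A rise in hemianopic detections could therefore reflect recovered field, a gaze shift, or both, and the planned data need not tell them apart. The existing safeguards reduce this risk without removing it.

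The direction is clear: added shifts after training inflate apparent recovery. The size is unknown. The illustrative 7, 13 or 20 points (shifts of 15, 30 or 45 degrees on one third of trials) rest on the assumptions listed in the check. The documents do not show that such shifts will occur, or that an observed improvement would be an artefact. In an exploratory study this should be fixed, and it is a cheap improvement rather than a fatal flaw.

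**What to change.** Under Peripheral Visual Field Test, replace *may* with *will*, and state that eye position is recorded at every frame test: baseline, post-training, 3 months and 6 months. The plan already provides for a camera or eye tracker and for a study-team member to review recordings. Specify in addition:

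1. A gaze tolerance around the fixation light, fixed in advance and necessarily below 15°, the azimuth of the nearest light. A trial is invalid if gaze leaves it at onset or before the press.
2. Trial-level scoring by the existing reviewer without knowledge of the visit.
3. Re-running invalid trials where possible, to keep 5 per location. This needs a check during the session; trials found invalid only on later review can no longer be repeated.
4. Fixation-valid trials for the primary percentage, all trials as a sensitivity analysis, and the share invalid reported at each visit.
5. Whether 0–1.5 seconds is an onset delay or a light duration.

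The cost is review of 55 trials per test: over 4 visits, 55 × 4 = 220 per subject, or 1,100 to 2,200 for 5 to 10 subjects. Some trials will be lost or repeated. If one third were invalid, that is about 8 of the 25 hemianopic trials, which is why re-running is better than dropping. The change has to be in place before baseline testing, since gaze not recorded then cannot be recovered.

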Grating Acuity Test - Visual acuity will be tested using a standard grating test. Subjects will be presented with a 10°x10° square window filled with either a horizontal or vertical grating, located 5° from the fixation point on a computer screen in their hemianopic or intact side. Gratings will start from 0.2 cycles per degree and progress to larger sizes of 0.5, 1.0, 1.5, 2.0, 2.5, 3.0, 4.0, then 5.0 cycles per degree. The test will comprise of 5 trials for each grating. Subjects will be asked to identify whether the grating is horizontal or vertical by either pushing buttons on a response pad or verbally. Responses will be recorded for each question.

Virtual Reality (Visual Field) Progress Test - At the end of each rehabilitation session, subjects will perform a brief 5-minute test using the VR system to

Color Vision Test - The color vision test will be administered on a computer. While focused on a central fixation point, subjects will be presented with a colored $10^\circ \times 10^\circ$ block located 5° in the anopic hemifield and be asked to verbally identify the color. A member of the research team will record these responses. The color in each trial will be randomly picked among the color choices of white, black, red, orange, yellow, green, blue, and violet. Each color will be displayed at least 3 times.

Shape Recognition Test - Subjects will be presented with basic shapes in their hemianopic side on a computer monitor. Shapes will be colored black and be displayed on a white background in a $10^\circ \times 10^\circ$ square window located 5° in the previously hemianopic side. Subjects will be asked to fixate on a central point and verbally identify each object or express uncertainty. Verbal responses will be recorded for later analysis. During this test, subject responses may be audiotaped in order to capture their responses. This test will consist of 20 trials.

Questionnaires

The NEI VFQ-25 and VA LV VFQ-48 questionnaires are designed to assess the taker's quality of life regarding limitations due to low vision.

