The virtual reality headset and headphones will provide visual and auditory stimulation used in the rehabilitation training. Each rehabilitation session will consist of 200 trials. At the end of each rehabilitation session, subjects will perform a brief 2-minute VR visual field progress test with the VR system to track rehabilitation progress. The rehabilitation will be considered complete once patients can reliably detect stimuli 45° in the hemianopic field.

If patients cannot detect stimuli at 15° by the end of 30 days of rehabilitation, they will repeat the rehabilitation for one more month, in order to determine if the slow progress or lack of progress is caused by simply not spending enough time performing rehabilitation.

Study Session 63: Post Rehabilitation Tests - Subject visual field did not increase (1 hour)

If no visual field improvement (measured by virtual reality visual field progress tests) has occurred at the end of the 2nd round of rehabilitation, subjects will complete one last visit, where they will be given the

NEI VFQ-25 and VA LV VFQ-48 questionnaires to complete. This visit will occur on the Wake Forest Baptist Medical Center campus.

Study Session 33: Post Rehabilitation Tests - Subject visual field increase (1.5 hours)

If a subject shows visual field expansion in the virtual reality visual field progress test, subjects will be given a **Peripheral Visual Field Test, NEI VFQ-25 and VA LV VFQ-48 Questionnaires** in order to measure visual field expansion and improvements in quality of life.

In previous animal studies, rehabilitated hemianopic animals could only detect spatial frequencies of 2 cycles/degree compared to over 5 cycles/degree in the (normal) intact animals. We hypothesize the subcortical visual pathway mediating the restored visual functions may not have the same capabilities as the visual cortex it is replacing. Therefore, recovered vision may have lower visual acuity. The different pathways involved in cross-modal rehabilitation may also affect abilities for shape recognition in the newly recovered visual field. We will explore whether this is the case with a simple **shape recognition test, visual acuity test, and color vision test** during this visit. Subjects will complete this visit on the Wake Forest Baptist Medical Center campus.

Study Session 34: Humphrey Visual Field Post-Intervention Test (1 hour)

Subjects will report to an optometrist for a **Humphrey Visual Field** perimetry test.

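### Acuity, colour and shape scores are labelled as recovered field, but the plan never confirms that their fixed 5° window was blind before training and sees after it

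*Combined protocol and SAP*

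**What the plan says.** Outcome Measure(s) gives the purpose of the three exploratory tests: "The qualities of recovered visual field will be examined with visual acuity, color recognition, and shape recognition tests after rehabilitation". Study Session 33 supplies the hypothesis behind them, that a subcortical pathway may do less than the cortex it replaces: "Therefore, recovered vision may have lower visual acuity".

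The location is fixed in each test's description:

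- Grating Acuity Test: a 10° × 10° patch of horizontal or vertical stripes, "located 5° from the fixation point on a computer screen in their hemianopic or intact side".
- Color Vision Test: a coloured 10° × 10° stimulus, the "block located 5° in the anopic hemifield and be asked to verbally identify the color".
- Shape Recognition Test: a 10° × 10° "square window located 5° in the previously hemianopic side".

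Field recovery is tracked elsewhere. The Peripheral Visual Field Test uses lights "located at azimuths of 15°, 30°, 45°, 60°, and 75°, as well as a center fixation light". The VR Progress Test uses 15°, 30° and 45°. Under Study Session 33, a subject receives the three tests if the VR test shows expansion. Study Session 1 lists the frame test and the two questionnaires at baseline, but no acuity, colour or shape test.

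The Humphrey test is a primary measure, compared before and after treatment, and is described as reaching 30°. The baseline visit (Session 2) may be replaced by a recent outside result. The post-training test is Session 34, numbered after the session with the three capability tests. The Analytical Plan mentions neither the Humphrey test nor the three capability tests by name.

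**The concern.** The label *recovered field* makes two claims about the place tested: that it was blind before training, and that it sees afterwards. The plan checks neither for the window it uses. The rule for entering these tests concerns 15° and beyond, while the window lies inside that limit.

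The error can run either way. If the inner field stayed blind while 15° and beyond recovered, low scores would be reported as a property of recovered vision. If the inner field was never lost, high scores would be credited to training. The second case is open because the selection criteria do not require blindness inside 15°, the screening text itself says that effects vary with the extent and location of damage, and no baseline run exists to reveal spared vision.

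At stake is what this exploratory outcome can conclude. The Sample Size section says the findings will be used to design future studies.

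**Working it through.** The plan gives no figure of its own on this point. The confidence interval in Sample Size concerns the success rate and does not enter here.

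**Inputs.** Window width 10° and position 5° (the three test descriptions); VR azimuths 15, 30, 45° (VR Progress Test); frame azimuths 15, 30, 45, 60, 75° and Humphrey limit 30° (Peripheral Visual Field Test).

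**Step 1: horizontal extent of the window.**

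- Centre at 5°: 5 − 10/2 = 0° to 5 + 10/2 = 10°.
- Near edge at 5°: 5° to 5 + 10 = 15°.

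**Step 2: compare with the tested places.**

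| Reading of 5° | Window | VR points inside | Frame points inside | Distance from outer edge to 15° | Within Humphrey 30° |
|---|---|---|---|---|---|
| Centre | 0–10° | 0 of 3 | 0 of 5 | 15 − 10 = 5° | Yes |
| Near edge | 5–15° | 0 of 3 | 0 of 5 | 15 − 15 = 0° (touches) | Yes |

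So VR expansion, and the frame test given at the same session, say nothing about the interior of the window. Of the field tests in the plan, only the Humphrey test covers it.

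**Step 3: what a score can mean.**

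| Window before → after | Poor score means | Good score means |
|---|---|---|
| Blind → seeing (recovered) | Limited recovered vision | Good recovered vision |
| Blind → blind | Field there did not recover | Not expected |
| Seeing → seeing | Pre-existing limitation | Vision never lost |

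Only the first row answers the stated question. Nothing in the plan assigns a subject to a row.

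**Step 4: can the grating test separate the rows by itself?** The series has nine steps: 0.2, 0.5, 1.0, 1.5, 2.0, 2.5, 3.0, 4.0 and 5.0 cycles/degree. Assume all five trials per step are on the blind side and the subject guesses between two orientations. The chance of 5 of 5 at a step is 0.5⁵ = 1/32 = 0.031. The chance of at least 4 of 5 is (5 + 1)/32 = 0.19. Passing every step from 0.2 to 2.0 cycles/degree (five steps) on the looser criterion has probability 0.1875⁵ ≈ 0.0002. A wholly blind window would therefore usually fail at the coarsest steps, whereas reduced acuity passes coarse gratings and fails fine ones. The series can thus help tell a blind window from a recovered one. It cannot tell recovered from never lost. Colour and shape have no such graded series.

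**The case against.** The strongest reply is that the inner field is not unmeasured. The Humphrey test is a primary outcome, is compared before and after training, and covers the window on either reading. Scores are interpreted at analysis, by which time the Session 34 map should be available, so its order after Session 33 matters little. This stands, and it rules out a reading that a reader might otherwise draw: that recovery is established only at 15° and beyond. What remains is that no text says the maps will be used this way.

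A reader might also infer that the placement would by itself generate the trial's hypothesis of poor acuity. The documents do not support that for gratings. The animal comparison is graded (2 against over 5 cycles/degree), and Step 4 shows that a blind window looks different. For shape and colour, subjects name what they see, and the shape test lets them say they are unsure, so blindness would tend to appear as non-detection. The ambiguity is still greater for those two tests than for gratings.

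Nor do the documents show that the window is in the wrong place. Recovery at 15–45° that leaves the inner field blind is possible but not shown. The background reports that training at 45° could reinstate the whole hemifield, and using 15° as the minimum sign of progress fits outward expansion.

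It would likewise be too strong to say that a pre-training run of the same tests could not help: failure before and success after would itself show gained function in the window.

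Gaze drift matters mainly on the centred reading. There, 1° of drift toward the blind side puts 1/10 of the window in the seeing half, which raises scores. With the near edge at 5°, drift must exceed 5° first.

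Finally, these are exploratory outcomes. That limits the weight of the point but does not remove it.

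**Conclusion.** The concern holds as a gap in confirmation. The plan reports three tests as qualities of recovered field without establishing, for any subject, that the window was blind before training and sees after it. On both readings of 5°, 0 of 3 VR azimuths and 0 of 5 frame azimuths lie inside the window.

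How often a window would be mislabelled cannot be computed, because the documents give no data on inner-field sparing or recovery. With five completers, each mislabelled subject is 1/5 = 20% of the description. Primary and secondary results are unaffected.

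The conclusion assumes that the window position is fixed for all subjects, since no text moves it. It also assumes that the Humphrey test places points under the window. The stated 30° reach implies this, but the point pattern is not given.

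**What to change.** 1. State whether 5° is the near edge or the centre of the window, and its vertical placement.
2. In the Analytical Plan, use the pre- and post-training Humphrey points under the window to classify each subject's window as recovered, still blind or always seeing. Fix beforehand the rule for a point to count as seen and the handling of windows with mixed points.
3. Report acuity, colour and shape as *recovered field* only for subjects whose window is classified as recovered. List the others separately with their class.
4. Optionally, for the grating test only, add a second window location at an azimuth missed at Session 1 and detected at Session 33, with the mirrored intact location as reference. This supplements the Humphrey classification: one light position with five trials does not show that a whole 10° window recovered. Colour and shape have no intact-side presentation to serve as reference.

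Items 1 to 3 need no new test or visit. Their cost is that fewer of the roughly five completers contribute to the recovered-field description. A baseline Humphrey from an outside record may also be less comparable, so its source and stimulus size should be recorded: Session 2 specifies size V, while Session 34 does not state a size. Item 4 adds some test time and software work, and screen size and viewing distance, which are not stated, would need checking. A baseline run of the three tests would also help, at the price of a longer first visit.
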